#### 1. SYNOPSIS

Title: A Prospective, Block Stratified Clinical Trial to Evaluate the Performance

and Operation of the Brevera Breast Biopsy System

**Device(s):** Study Device: The Hologic Brevera Breast Biopsy System with CorLumina

**Imaging Technology** 

Control: Current standard-of-care breast biopsy procedure devices

**Objective:** To obtain clinical/operational data and feedback on the Brevera Breast

Biopsy System as compared to the current standard-of-care breast biopsy

procedures

**Design:** Prospective, multi-center, block stratified, controlled clinical trial

**Primary Outcome:** To obtain data on the operation and feedback from the perspective of the

clinician(s), patients, and technologist(s) using the systems.

Planned Enrollment: Up to 525 subjects

**Number of Sites:** Up to 10 sites in the United States

**Population:** Women with suspicious findings on previous imaging (e.g.

mammographic, Magnetic Resonance Imaging or Conventional Diagnostic Ultrasound imaging (screening or Diagnostic)) who are sent for biopsy.

**Follow-up Schedule:** No follow-up is required of subjects after the procedure and associated

data collection.

**Clinical Trial Duration** 

(Estimated):

Clinical Trial Start: Q3/2017
Enrollment Completion: Q1/2018
Last Patient, Last Visit: Q1/2018
Final Report: Q2/2018

Inclusion Criteria: 1) Female aged 18 years of age or older

2) Subject has at least one breast imaging finding requiring biopsy for

which images are available

3) Subject is able to understand, read and sign the trial specific informed consent form after the nature of the trial has been fully explained to

her

**Exclusion Criteria:** 

- Patients who, based on the physician's judgement, may be at increased risk or develop complications associated with core removal or biopsy.
- 2) Patients receiving anticoagulant therapy or may have bleeding disorders which may put the patient at increased risk of procedural complications based upon physicians judgement

**Sponsor:** Hologic, Inc.

#### 2. INTRODUCTION

The Brevera Breast Biopsy System integrates tissue acquisition, real time imaging, and post biopsy handling all during the same procedure. This device has received FDA 510k Clearance (K163052). All commercial breast biopsy devices will be utilized according to the product's Instructions for Use.

# 2.1 Summary of Animal Testing Data

In July 2016, Hologic conducted an animal study titled, "GLP Acute Evaluation of the Brevera Vacuum-Assisted Breast Biopsy System in the Porcine Model."

The objective of that study was to support, using attribute data, that the Gen 2 system adequately performs the following functions using tissue in an animal model:

- 1. Acquire core tissue samples from the biopsy site.
- 2. Transport tissue samples into the filter wheel.
- 3. Capture X-ray images of transported tissue cores in the tissue filter.

The results of the above referenced study demonstrated that the device performed to the intended specifications and passed validation for procedures in humans.

## 2.2 Device Description

The Brevera Breast Biopsy System with CorLumina imaging technology is a vacuum-assisted biopsy device, which is used to remove breast tissue in a minimally invasive manner using stereotactic or tomosynthesis imaging. The system is designed for biopsy and for radiographic image acquisition and display only. The biopsy device will come in contact with tissues and/or body fluids.

The Brevera biopsy needle is single-use and is disposable. The user connects the biopsy needle to a reusable device driver and connects the biopsy device components to the console. The biopsy needle primarily consists of a hollow needle with a side aperture and a sharpened inner cannula that, when connected to the Brevera breast biopsy system, rotates and extends across the aperture to acquire targeted tissue. The Brevera device driver contains mechanical and electrical components that drive needle rotation and advancement. During the biopsy process, vacuum created inside the biopsy device pulls tissue into the aperture. The cannula translates and rotates to cut the tissue. The tissue sample is then aspirated through a tubing line to a tissue filter. Saline is supplied through the biopsy device to lavage the cavity and deliver tissue to the tissue filter.

When the Brevera biopsy needle is connected to the Brevera device driver, the combination is referred to as the Brevera breast biopsy device.

An introducer system, specifically designed for use with the Brevera breast biopsy system, is packaged with the biopsy needle. This introducer maintains access to the targeted area of interest and allows for deployment of a biopsy site marker. The introducer is used to control the variable aperture function of the device. The introducer also prohibits the user from administering medication through the Y-site in the tubing while the device is in the armed (pre-fire) position. The Brevera breast biopsy system with CorLumina imaging technology acquires and displays the radiographic images of core specimens contained in the tissue filter. A tissue filter, specifically designed for use with the Brevera breast biopsy system, is provided with the biopsy needle.

The Brevera breast biopsy system with CorLumina imaging technology also has the capability to display images as well as to transfer these images to external devices. The images acquired with this system are intended to confirm removal of tissue from a suspected lesion or pathology. The system is not intended for diagnostic purposes.

Radiology technologists, surgical personnel, surgeons, radiologists, and pathologists can use the specimen radiography equipment in the Brevera breast biopsy system with CorLumina imaging technology.

[figure not shown]

Figure 1: Brevera Breast Biopsy System with CorLumina Imaging Technology System

Overview

# Figure Legend

- 1. Biopsy device
- Remote control for mode control and arming or firing the biopsy device
- 3. Technologist display
- 4. Imaging display
- 5. Vacuum line assembly and suction canister
- 6. Tissue filter assembly
- 7. Tissue filter drawer
- 8. Footswitch
- 9. Power cord

The user interface for data entry, patient selection, and image acquisition and review is on the Imaging display. The user interface for controlling the modes of the biopsy device are buttons on the Technologist display and on the remote control device. The user interface for arming and firing the biopsy device is on the remote control device. The user rotates the aperture on the biopsy device with the thumbwheel on the disposable biopsy needle. The user adjusts the size of the aperture on the biopsy device by assembling the introducer in one of two preset positions along the needle shaft.

The control devices for this study will be the current devices already used for breast biopsy procedures.

## 2.3 Device Accountability

The Hologic operations team will keep records to document the shipment and installation of the commercial Brevera system. The Principal Investigator or an authorized designee shall keep records documenting the type, and use of the devices.

# 2.4 Intended Use/Current Indication for Use

See product specific Instructions for Use.

# 2.5 Device Procedure(s)/Training

Prior to use in clinical procedures and the implementation in the standard practice, technologists and clinicians will be trained by a Hologic representative on the use of the new Brevera device (according to Instructions for Use) and the features. This training will cover quality control procedures as well as didactic training on the equipment. The investigators selected for this trial have previous experience with breast biopsy core sampling.

## 3. TRIAL JUSTIFICATION

This trial will be performed to obtain clinical/operational data and feedback on the Brevera Breast Biopsy System as compared to the current standard-of-care breast biopsy procedures

## 4. POTENTIAL RISK/BENEFIT

## 4.1 Potential Clinical Benefit

There are no clinical benefits to the patient. The results learned from this trial could help future patients.

Patients scheduled for a biopsy will still undergo a breast biopsy procedure if they choose not to participate in this trial. The biopsy may be performed with the Brevera or other commercially available system used by the site.

# 4.2 Anticipated Adverse Device Effect(s)

Common risks associated with the use of any commercial biopsy system are limited to the region surrounding the biopsy site and include:

- Bruising and swelling of the breast
- Infection or bleeding at the biopsy site
- Altered breast appearance, depending on how much tissue is removed and how your breast heals

Excessive pain following the procedure at the biopsy site

All of the incidents listed above are related to biopsy procedures and not necessarily the devices themselves.

#### 4.3 Risk Benefit Rationale

This clinical trial is justified because Hologic and clinical investigators believe the potential benefits outweigh the potential risks of trial participation. There are no additional risks known for the commercially available devices.

#### 5. TRIAL DESIGN

# 5.1 Trial Objective(s)

The objective of this trial is to obtain clinical/operational data and feedback on the Brevera Breast Biopsy System relative to current standard-of-care breast biopsy systems; and to evaluate potential clinical advantages conferred by the use of the Brevera Breast Biopsy System, such as reduced procedure time.

## 5.2 Primary Endpoint

The primary endpoint of this trial is the measured difference in procedure time between biopsies performed with the Brevera biopsy system with real time imaging and biopsies performed using the standard-of-care biopsy system at each clinical site.

# 5.3 Secondary Endpoint(s)

Secondary endpoints to be evaluated in this trial include differences in post-biopsy complication rates, total tissue acquisition by number of cores and sample mass, total tissue used by pathology for diagnosis, and the number of discordant biopsies.

## 5.4 Trial Design

Prospective, multi-center, block stratified controlled clinical trial. This trial will include collection of the breast imaging exams (both screening and diagnostic work up) leading up to the breast biopsy procedure, which may include mammograms, ultrasound or MRI images as applicable.

The trial procedure will roll out in two phases: 1) a run-in phase consisting of five (5) procedures aimed at familiarizing participating radiologists with the Brevera Breast Biopsy System; and 2) an analysis phase consisting of a block-randomized acquisition of twenty (20) sequential acquisitions utilizing both standard-of-care biopsy system at each site and the Brevera Breast Biopsy System.

#### 5.4.1 Phase 1 (Run-in Phase)

After obtaining subject informed consent, each radiologist participating in the study will initially use the Brevera Breast Biopsy system for enrollment of his or her first five (5) cases. The run-phase will allow

each participating radiologists to become familiar with the use of a new device. The five (5) cases per radiologist completed will be compared to the Brevera cases completed in Phase 2 for the same outcomes listed in sections 5.2 and 5.3 above so as to provide informational data related to the training and adoption of the Brevera Breast Biopsy System.

Once a clinician has completed his or her initial five (5) run-in cases, they may begin phase 2 of the study. Note that each individual radiologist participating in the study must complete their initial five (5) cases prior to beginning Phase 2; however, each individual participant may complete the initial five (5) cases at different times. Example: it may be expected that the first participating radiologist at a given site may begin in phase 2 while the second and/or third participating radiologist at the same site in the study are still completing their five run-in cases.

# 5.4.2 Phase 2 (Block Stratification Phase) -

Each individual radiologist will enroll a maximum of twenty (20) subjects, and a maximum of three (3) radiologists may participate in this study from each representative study site. After a radiologist completes his or her five (5) cases with Brevera in Phase (1), each site will begin to sequentially enroll subjects based on a block-stratified randomization. Subjects will either be enrolled to have their biopsy procedure performed using current standard-of-care breast biopsy procedures at the site or Brevera Breast Biopsy procedures based on the block diagram given in Figure.

Randomization of enrollment will be determined prior to study start-up and provided to each site. Each radiologist will enroll 20 total subjects as part of the block stratification phase as defined in Figure 2.

[figure not shown]

Figure 2: Study Design Outline

Case Report Forms related to procedural data and surveys have been created in order to obtain information related to feedback from the clinician(s), patient, and technologist(s). The surveys include questions that relate to the overall feel and aesthetic of the product as well at the overall performance of the breast biopsy system. The questionnaires will be given to the clinician(s), patient, and the technologist(s) at the conclusion of the procedure and will be focused for each target group. Once a patient has completed the breast biopsy procedure, her direct participation in the trial is concluded. There are no follow-up visits required for participation in this trial..

Surveys will be collected via paper forms to capture the questionnaire data, and subsequently abstracted into an Electronic Data Capture (EDC) system. The results of the survey questions and images obtained will be compiled and used to support marketing claims and publications, as applicable.

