#### 5.7.2 Exclusion Criteria

- 1) Patients who, based on the physician's judgement, may be at increased risk or develop complications associated with core removal or biopsy.
- 2) Patients receiving anticoagulant therapy or may have bleeding disorders which may put the patient at increased risk of procedural complications based upon physicians judgement.

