#### 6. TRIAL PROCEDURES

The trial will collect de-identified case report form data and patient images from biopsy procedures. This will include collection of images from the prior exam leading up to the breast biopsy procedure. The biopsy procedures will be done consistent with current clinician direction/standard-of-care.

Prior to use of the new Brevera Breast Biopsy System, normal applications training will take place in order to train the users on new features and quality control testing.

Patients will be enrolled using a block randomization. Each clinician will complete ten (10) patients in block 1 and ten (10) patients in block 2. (Blocks will be defined as either the Standard-of-care biopsy system or the Brevera Biopsy system). A clinician must complete block 1 before moving on to block 2.

[figure not shown]
Clinical data will be collected on the procedure within each block by patient procedure. The procedures will collect data related to time of procedure, number of cores collected, post biopsy results and survey data on the system.

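### Device assignments are known before women are enrolled and nothing records who was passed over, so selective enrolment could bias the procedure-time comparison undetected

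*Combined protocol and SAP*

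**What the plan says.** - **Allocation (Section 5.4.2).** "Randomization of enrollment will be determined prior to study start-up and provided to each site". The same section makes the operator the enroller: "Each radiologist will enroll 20 total subjects as part of the block stratification phase as defined in Figure 2".
- **Order (Section 6).** "Each clinician will complete ten (10) patients in block 1 and ten (10) patients in block 2". On what a block is: "Blocks will be defined as either the Standard-of-care biopsy system or the Brevera Biopsy system". On sequence: "A clinician must complete block 1 before moving on to block 2".
- **Eligibility (Section 5.7.2).** The first criterion excludes "Patients who, based on the physician's judgement, may be at increased risk or develop complications associated with core removal or biopsy". The second, on anticoagulants and bleeding disorders, also turns on the physician's judgement. Section 5.7.4 lets the investigator discontinue a subject on judgement.
- **Enrolment (Sections 5.4, 5.4.2 and 5.7.3).** Intake is described as sequential, and a woman counts as enrolled once she signs the consent form.
- **Analysis (Sections 5.2 and 8).** The primary endpoint is the difference in procedure time. It is analysed by mixed effects regression with device, habitus and a yes/no lesion location (near the chest wall or axilla) as fixed effects, and site and radiologist as random effects.

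The readable text describes no concealment of the next assignment, no assignment after consent, and no screening log. Figure 2 and the figure in Section 6 are not available, but the text of Section 6 on block order is explicit.

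**The concern.** Randomisation protects a comparison only if the person deciding whom to enrol cannot foresee the assignment. Here the enroller is the operator, can foresee it, and has discretion over eligibility. A radiologist who expects a difficult case may, without any intent to mislead, not approach that woman while one device is in use. During block 1 the radiologist could also wait until block 2 begins.

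The two devices would then be compared on different case mixes, and part of any time difference would reflect selection. Section 5.4.2 says that results may support marketing claims and publications, so a small spurious difference matters.

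This is separate from the confounding of device with calendar time that contiguous blocks also create. Selection could occur even if nothing changed over time.

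**Working it through.** **1. How many assignments are foreseeable.** Each radiologist has 20 Phase 2 cases in two single-device blocks of ten, with block 1 completed first.
- If the radiologist sees the site's list, 20 of 20 are known.
- If not, the first case of block 1 reveals its device, which fixes the other 9 in that block and all 10 in block 2: 19 of 20. Guessing the first at 50% gives (19 + 0.5)/20 = 97.5% correct.

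**2. The plan's own power figure.** Inputs from Section 8: 7 sites × 3 radiologists × 20 = 420 subjects, so 210 per device; difference 3 min; SD 12 min; intraclass correlation 0.150; alpha 0.05 (sidedness not stated, two-sided assumed). Device is compared within radiologist, so the residual SD is 12 × √(1 − 0.15) = 11.06 min.
- SE = 11.06 × √(2/210) = 1.08 min.
- Power = Φ(3/1.08 − 1.96) = 79.4%, which matches the stated figure of approximately 80%.

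**3. Effect of a case-mix shift.** With no true device effect and a net shift of b minutes, the false-positive rate is Φ(b/SE − 1.96) + Φ(−b/SE − 1.96). The documents give no value for b, so the following are assumptions. Suppose 5% to 10% of cases would run 10 to 15 min longer and are kept out of one device's block only. If every radiologist did this against the same device, b would be 0.05 × 10 = 0.5 to 0.10 × 15 = 1.5 min.

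| Assumed pattern across the 21 radiologists | Net shift b (min) | False-positive rate |
|---|---|---|
| All select against the same device | 0.5 to 1.5 | 7.5% to 28.5% |
| Half do so, the rest do not select | 0.25 to 0.75 | 5.6% to 10.7% |
| Two-thirds against one device, one-third against the other | 0.17 to 0.5 | 5.3% to 7.5% |

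These figures take long cases as perfectly identified in advance and give no credit for covariate adjustment.

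**4. A second assumed model, with imperfect prediction.** The hardest fraction q of expected cases is kept out of one block, and predicted difficulty correlates ρ with actual time. The shift is ρ × 11.06 × φ(z)/(1 − q), where z is the (1 − q) normal quantile. With q from 5% to 20% and ρ from 0.3 to 0.7, the shift is 0.36 to 2.71 min and the rate 6.3% to 70.9%. At q = 10% and ρ = 0.5 they are 1.08 min and 17.0%. This model also assumes the same direction for every radiologist. The width of the range shows that the documents do not determine the size.

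**5. What the model in Section 8 can remove.** It removes selection acting through habitus or chest wall/axilla location. It does not remove selection through other features, such as lesion visibility or the expected number of cores. Radiologist random effects do not help, because the selection would occur between two blocks of the same radiologist.

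**The case against.** Several objections have force.

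- **Enrolment is sequential.** Sections 5.4 and 5.4.2 say so, and skipping or deferring cases sits badly with that wording. This stands as a partial safeguard. But it orders the women who are enrolled; it does not say that every eligible woman must be approached, and no log would show whether she was.
- **The list goes to the site.** A reader might infer that each radiologist holds it and knows all 20 assignments. Section 5.4.2 names only the site. The block order in Section 6 still reveals 19 of 20.
- **Women outside the trial.** Section 4.1 says: "The biopsy may be performed with the Brevera or other commercially available system used by the site". A reader might take this as a route for women whom a radiologist passes over. The sentence before it is about women who choose not to take part, so it does not support that reading.
- **The exclusions concern risk, not duration.** Nothing in the documents says that women at higher risk have longer procedures. The criteria show discretion in enrolment; the link to procedure time is an inference.
- **The model adjusts for case mix.** It does in part, so a claim that it cannot remove the bias would go too far.
- **Devices cannot be blinded.** True, but concealing the next assignment until enrolment does not require blinding.

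**Conclusion.** The point holds as a weakness of design. Followed as written, the plan lets at least 19 of 20 assignments per radiologist be foreseen by the person who enrols, and it has no means of showing whether selection took place.

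A reader might go further and conclude that the result will be biased, or by a particular share of the 3-minute target. The documents support neither: they give no information on how often cases would be withheld, by whom, or in which direction. The illustrative range of 0.25 to 1.5 min (5.6% to 28.5% false positives) rests on the assumed frequencies and extra minutes, perfect prediction of long cases, no gain from covariates, and selection in one direction by at least half the radiologists. Opposite directions would make it smaller. The change is worth making because it is cheap, not because a bias of known size has been shown.

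**What to change.** In Sections 5.4.2 and 6:

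1. Keep ten cases per device for each radiologist, but replace the contiguous blocks with one randomly permuted 10:10 list per radiologist. With past assignments known, the best guess is right about 62% of the time under such a list, against about 68% for permuted blocks of 4 or 6 and 50% by chance. Short blocks are therefore the weaker choice for an unblinded operator.
2. Release each assignment by sealed, sequentially numbered opaque envelope only after consent, eligibility, habitus and lesion location are recorded. Electronic release would also serve if the data capture system supports it; Section 5.4.2 describes that system only as receiving data from paper forms.
3. Keep a dated log of eligible women not enrolled, with the reason and the device then due. Under concealed release, the device should be filled in afterwards.
4. If contiguous blocks are retained for logistics, keep the log, report it by device, and state that assignment was not concealed.

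**Cost.** Sample size, 10:10 balance and nominal power do not change. There is minor administrative work and more switching of devices between cases, which may itself affect procedure time. Section 5.4.1 expects radiologists at one site to be in different phases at once, so both systems may be needed in parallel anyway; that does not show that switching case by case is easy. Interleaving would also reduce the calendar-time confounding noted above.
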